- Grade 4 post-injection reaction (PIR) within 7 days after any study injection
- Clinically significant Grade 3 or higher systemic reaction (eg, angioedema, generalized urticaria) within 7 days after any study injection
- Grade 3 or 4 hypotension within 24 hours of any study injection
- Grade 3 or 4 respiratory reaction or symptoms occurring within 24 hours of any study injection
- Any life-threatening AE, regardless of relationship to study drug
- Any AMI
- Any confirmed immune-mediated AE
- Violation of protocol eligibility criteria
- Subject received prohibited medications
- SAE assessed as a suspected adverse reaction (SAR) or adverse reaction (AR)
- Subject becomes pregnant or begins breastfeeding

If the subject is not eligible for subsequent study injections, **the subject will not be withdrawn from the study**, but, if possible, will be followed for safety through End-of-Study (EOS) Visit.

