9.4.4 Post-Injection Reaction Assessments

Assessments of PIRs ([Section 10.2](#)) will be collected for a minimum of 30 minutes following each study injection at the clinical site.

On Day [REDACTED] subjects will be asked to complete an e-diary (or equivalent) to record any solicited local (pain, redness, pruritus [itchiness], and swelling at the injection site) and solicited systemic signs and symptoms (fatigue, temperature, chills, malaise, myalgia, gastrointestinal symptoms, and headache) during the 7-day follow-up period after vaccination. The severity of the post-injection reactions will be graded using the Toxicity Grading Scale for Healthy Adult and Adolescent Volunteers Enrolled in Preventive Vaccine Clinical Trials ([Appendix 2](#)).

PIRs persisting beyond 7 days after each study injection are considered AEs and should be recorded and reported as AEs. These will be included in the electronic data capture (EDC) AE dataset.

PIRs inadequately recorded by the subject in the e-diary and occurring during the diary period from Day 1 through Day 7 following each study injection can be reconstructed by the investigator in the AE CRF page. These will be included in the EDC AE dataset.

Refer to the eCRF completion guidelines for additional details.

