10.10 Adverse Event Severity and Relationship to Study Treatment

10.10.1 Severity Grading of Adverse Events and Abnormal Laboratory Test Results

The severity of AEs and laboratory abnormalities will be graded based on the United States Food and Drug Administration's (FDA) Guidance for Industry: Center for Biologics Evaluation and Research (CBER) Toxicity Grading Scale for Healthy Adult and Adolescent Volunteers Enrolled in Preventive Vaccine Clinical Trials in [Appendix 2](#), with the modification that, by convention, all fatal AEs will be graded as Grade 5 (Fatal).

All AEs not listed in the CBER toxicity grading scale will be graded as shown in [Table 10-1](#).

Table 10-1: Grading Scale for Adverse Events Not Included in the CBER Guidance on Toxicity Grading for Healthy Volunteers in Vaccine Clinical Trials

AE Severity	Definition
Grade 1 – Mild	No interference with activity
Grade 2 – Moderate	Some interference with activity, not requiring medical intervention
Grade 3 – Severe	Prevents daily activity and requires medical intervention
Grade 4 – Potentially life-threatening	Emergency room visit or hospitalization
Grade 5	Death

CBER = Center for Biologics Evaluation and Research.

For all AEs and SAEs, if there is a change in the severity after the event onset, the event should be reported as a single entry with the maximum severity grading captured.

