Pain	Does not interfere with activity	Repeated use of non-narcotic pain reliever > 24 hours or interferes with activity	Any use of narcotic pain reliever or prevents daily activity	Emergency room (ER) visit or hospitalization
Tenderness	Mild discomfort to touch	Discomfort with movement	Significant discomfort at rest	ER visit or hospitalization
Erythema/Redness ^a	2.5 – 5 cm	5.1 – 10 cm	> 10 cm	Necrosis or exfoliative dermatitis
Induration/Swelling ^b	2.5 – 5 cm and does not interfere with activity	5.1 – 10 cm or interferes with activity	> 10 cm or prevents daily activity	Necrosis
Pruritus ^c	No interference with activity	Some interference with activity, not requiring medical intervention	Prevents daily activity and requires medical intervention	ER visit or hospitalization
Systemic Reactions				
Fever (°C)	38.0 – 38.4	38.5-38.9	39.0-40	>40
Myalgia	No interference with activity	Some interference with activity	Significant: prevents daily activity	ER visit or hospitalization
Fatigue	No interference with activity	Some interference with activity	Significant: prevents daily activity	ER visit or hospitalization
Malaise	Uneasiness or lack of well being	Uneasiness or lack of well being; limiting instrumental ADL	A grade is not available	A grade is not available
Chills ^c	No interference with activity	Some interference with activity, not requiring medical intervention	Prevents daily activity and requires medical intervention	ER visit or hospitalization
Nausea/vomiting	No interference with activity or 1 – 2 episodes/24 hours	Some interference with activity or > 2 episodes/24 hours	Prevents daily activity, requires outpatient IV hydration	ER visit or hospitalization for hypotensive shock
Diarrhea	2 – 3 loose stools or < 400 gms/24 hours	4 – 5 stools or 400 – 800 gms/24 hours	6 or more watery stools or > 800gms/24 hours or requires outpatient IV hydration	ER visit or hospitalization

	Mild (Grade 1)	Moderate (Grade 2)	Severe (Grade 3)	Potentially Life Threatening (Grade 4)
Headache	No interference with activity	Repeated use of nonnarcotic pain reliever > 24 hours or some interference with activity	Significant; any use of narcotic pain reliever or prevents daily activity	ER visit or hospitalization
Systemic Illness				

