Illness or clinical adverse event (as defined according to applicable regulations)	No interference with activity	Some interference with activity not requiring medical intervention	Prevents daily activity and requires medical intervention	ER visit or hospitalization

Source: ([Center for Biologics Evaluation and Research 2007](#)).

ER = emergency room; IV = intravenous.

^a In addition to grading the measured local reaction at the greatest single diameter, the measurement should be recorded as a continuous variable.

^b Induration/swelling should be evaluated and graded using the functional scale as well as the actual measurement

^c Not part of CBER grading scale.

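### Appendix 2 stops malaise at Grade 2 without a stated reason, so malaise alone cannot meet the graded safety rules, yet SAP 8.7 gives it a severe class

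*Protocol*

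**What the plan says.** Protocol 9.4.4 has subjects record, for 7 days after vaccination, "solicited systemic signs and symptoms (fatigue, temperature, chills, malaise, myalgia, gastrointestinal symptoms, and headache". The same section and 10.2 grade these reactions with the scale in Appendix 2.

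In the malaise row of Appendix 2, the highest defined level is Grade 2: "Uneasiness or lack of well being; limiting instrumental ADL". The Grade 3 and Grade 4 entries both read "A grade is not available". Malaise carries no footnote, and no text elsewhere explains the limit. In the fatigue and myalgia rows, Grade 3 is "Significant: prevents daily activity", and Grade 4 is an emergency-room visit or a hospital admission.

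Four listed criteria depend on Grade 3 or 4:
- Protocol 5.3: stop dosing a subject after a Grade 4 post-injection reaction.
- Protocol 5.3: stop dosing after a "Clinically significant Grade 3 or higher systemic reaction" within 7 days.
- Protocol 8.2: pause dosing of all subjects for Grade 3 or higher solicited reactions in at least two subjects, with further conditions.
- Protocol 10.1: report a treatment-related Grade 3 event to the sponsor within 24 hours.

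SAP 8.7 says that reactions are graded with the CBER scale. It then places malaise with eight other symptoms in a scheme of none, mild, moderate and severe, where severe means that daily activity is prevented.

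**The concern.** A subject kept from normal activity by malaise gets Grade 2 at most. A subject equally disabled by fatigue gets Grade 3. The discontinuation, pause and expedited-report criteria are written in grades, so the two subjects are handled differently by rule although the burden is the same.

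Protocol 2.4.2 states that there are no clinical data on adding CpG 1018 to this antigen, which makes rule-based safeguards more useful than usual. Reactogenicity is also a secondary endpoint in both parts, and the SAP table for malaise will have a severe row whose meaning is unclear.

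**Working it through.** The plan gives no figure on this point, so there is none to reproduce. The check is a count and a comparison of texts.

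**Step 1. Rows in Appendix 2.** Local: pain, tenderness, redness, swelling, pruritus = 5. Systemic: fever, myalgia, fatigue, malaise, chills, nausea/vomiting, diarrhea, headache = 8. Total 5 + 8 = 13. Rows with Grades 3 and 4 defined: 12. Rows without: 13 − 12 = 1 (malaise). Pruritus and chills have all four grades although a footnote marks them as "Not part of CBER grading scale". Absence from the source scale is therefore not, in this table, a reason to leave grades out.

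**Step 2. Same burden, different grade.**

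| Event | Malaise | Fatigue or myalgia |
|---|---|---|
| Daily activity prevented | at most Grade 2 | Grade 3 |
| Emergency-room visit, event not serious | at most Grade 2 | Grade 4 |

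**Step 3. The rules.** The highest malaise grade is 2. The lowest grade that the four criteria accept is 3 (4 for the first criterion in 5.3). Since 2 < 3, malaise alone meets none of them. An emergency-room visit does not by itself make the event serious, because 10.9.1 says that it does not count as hospitalization. It could still be judged an important medical event.

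**Step 4. Possible fallbacks.**
- Table 10-1. Section 10.10.1 limits it: "All AEs not listed in the CBER toxicity grading scale will be graded as shown in" that table. Malaise has its own row in Appendix 2.
- The general illness row in Appendix 2. Its Grade 3 is "Prevents daily activity and requires medical intervention", so disabling malaise without intervention still misses it. Its Grade 4 would fit an emergency-room visit, but nothing directs an investigator there for a symptom that has its own row.
- Malaise lasting beyond 7 days becomes an adverse event, but 10.10.1 grades adverse events with Appendix 2 as well, so the limit stays.

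**Step 5. SAP 8.7.** The activity scheme covers pain, pruritus, fatigue, chills, malaise, myalgia, vomiting, diarrhea and headache = 9 symptoms. Compared with Grade 3 in Appendix 2:
- Prevented activity is enough: pain, fatigue, myalgia, headache = 4.
- Grade 3 exists but has other or further conditions: pruritus and chills (medical intervention as well), vomiting (intravenous hydration), diarrhea (stool count, volume or hydration; no activity criterion) = 4.
- No Grade 3 exists: malaise = 1.

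4 + 4 + 1 = 9. If Appendix 2 governs, the severe row for malaise is zero by construction. If the SAP wording governs, the report can show severe malaise that the protocol could not grade as severe and that met no graded rule.

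**The case against.** The strongest reply is that little is lost in practice, and most of it stands. Malaise overlaps with fatigue and myalgia, which are in the same diary and can reach Grades 3 and 4. Serious and life-threatening events have separate rules in 5.3 and 8.2. The 5.3 list is introduced as inclusive, not exhaustive, and the examples for its Grade 3 item (angioedema, generalized urticaria) point to hypersensitivity. The 8.2 criterion also needs two subjects, more than 48 hours and a DMC judgement of clinical significance, so it rests partly on discretion for every symptom. The DMC may review safety data at any time (4.1), and the investigator may withdraw a subject in that subject's interest (5.4).

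It can also be said that Table 10-1 might apply if the CBER source does not list malaise. The documents do not settle this. The malaise row lacks the footnote that marks additions to that scale, which speaks against it. If Table 10-1 did apply, an emergency-room visit for malaise would be Grade 4, but disabling malaise without medical intervention would still miss Grade 3.

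Two stronger readings are tempting and are not supported. A reader might infer that disabling malaise escapes safety oversight altogether; the routes above show that it does not. A reader might also infer that malaise is the only symptom for which SAP 8.7 and Appendix 2 disagree. Step 5 shows four others whose Grade 3 differs from the SAP severe wording. What is particular to malaise is that no Grade 3 or 4 exists at all.

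**Conclusion.** The point holds as a minor inconsistency that is cheap to correct. One of 13 reaction rows lacks Grades 3 and 4 without a stated reason. Non-serious malaise alone cannot meet the listed graded criteria in 5.3, 8.2 and 10.1, and the SAP severe class for malaise has no protocol grade behind it.

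The rules cover all of the roughly 200 subjects, but the documents give no malaise rate, so no number of affected events can be stated. Severe events may be few. Protocol 2.4.2.1.2 describes two vaccines with CpG 1018 plus alum as having no severe adverse reactions, though with another antigen and 750 or 1500 mcg of CpG 1018, against 3000 mcg here.

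The conclusion assumes that the malaise row in Appendix 2 governs. The e-diary and the eCRF completion guidelines are not among the documents, so the scale that subjects see cannot be checked. The documents do not show whether the limit is an oversight or intended.

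**What to change.** In Appendix 2, replace the two empty malaise grades with the definitions used for fatigue and myalgia: Grade 3 "Significant: prevents daily activity", and Grade 4 an emergency-room visit or hospital admission. Use the same definitions in the e-diary. The existing severe class for malaise in SAP 8.7 then agrees with the protocol, and 5.3, 8.2 and 10.1 need no edit.

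Do not add a Grade 4 class in SAP 8.7 for malaise alone, because the other eight symptoms in that scheme have none. Add it for all nine or for none. If the limit on malaise is intended, state the reason and remove the severe class for malaise from SAP 8.7; this settles the conflict but leaves the gap in the rules.

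Cost: two table entries and matching diary text. The downside is that a few more events may count as Grade 3 or 4.

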APPENDIX 3: LIST OF AUTOIMMUNE CONDITIONS AND TERMS OF SPECIAL INTEREST

Any of the conditions listed below that are newly occurring after vaccination are to be categorized as an AESI. In addition, subjects with any of the conditions listed below are excluded from the study^a.

Gastrointestinal disorders

- Celiac disease
- Crohn's disease
- Ulcerative colitis
- Ulcerative proctitis

Liver disorders

- Autoimmune cholangitis
- Autoimmune hepatitis
- Primary biliary cirrhosis
- Primary sclerosing cholangitis

Metabolic diseases

- Addison's disease
- Autoimmune thyroiditis (including Hashimoto thyroiditis)
- Diabetes mellitus type 1
- Grave's or Basedow's disease

Musculoskeletal disorders

- Antisynthetase syndrome
- Dermatomyositis
- Juvenile chronic arthritis (including Still's disease)
- Mixed connective tissue disorder
- Polymyalgia rheumatic
- Polymyositis
- Psoriatic arthropathy
- Relapsing polychondritis
- Rheumatoid arthritis
- Scleroderma, including diffuse systemic form and CREST syndrome
- Spondyloarthritis, including ankylosing spondylitis, reactive arthritis (Reiter's Syndrome) and undifferentiated spondyloarthritis
- Systemic lupus erythematosus
- Systemic sclerosis

Neuroinflammatory disorders

- Acute disseminated encephalomyelitis, including site specific variants: eg, non-infectious encephalitis, encephalomyelitis, myelitis, myeloradiculomyelitis
- Cranial nerve disorders, including paralyses/paresis (eg, Bell's palsy)
- Guillain-Barré syndrome, including Miller Fisher syndrome and other variants
- Tolosa Hunt syndrome^b
- Immune-mediated peripheral neuropathies and plexopathies (including chronic inflammatory demyelinating polyneuropathy, multifocal motor neuropathy and polyneuropathies associated with monoclonal gammopathy)
- Multiple sclerosis
- Myasthenia gravis, including Eaton-Lambert syndrome
- Narcolepsy
- Optic neuritis
- Transverse Myelitis

Skin disorders

- Alopecia areata
- Autoimmune bullous skin diseases (including pemphigus, pemphigoid and dermatitis herpetiformis)
- Cutaneous lupus erythematosus
- Erythema nodosum
- Morphoea
- Lichen planus
- Psoriasis
- Rosacea
- Sweet's syndrome
- Vitiligo

Vasculitides

- Large vessels vasculitis including: giant cell arteritis such as Takayasu's arteritis and temporal arteritis
- Medium sized and/or small vessels vasculitis including: polyarteritis nodosa, Kawasaki's disease, microscopic polyangiitis, Wegener's granulomatosis, Churg-Strauss syndrome (allergic granulomatous angiitis), Buerger's disease (thromboangiitis obliterans), necrotizing vasculitis and anti-neutrophil cytoplasmic antibody (ANCA) positive vasculitis (type unspecified), Henoch-Schonlein purpura, Behcet's syndrome, leukocytoclastic vasculitis

Others

- Antiphospholipid syndrome
- Autoimmune hemolytic anemia
- Autoimmune glomerulonephritis (including IgA nephropathy, glomerulonephritis rapidly progressive, membranous glomerulonephritis, membranoproliferative glomerulonephritis, and mesangioproliferative glomerulonephritis)
- Autoimmune myocarditis/cardiomyopathy
- Autoimmune thrombocytopenia
- Goodpasture syndrome
- Idiopathic pulmonary fibrosis
- Pernicious anemia
- Raynaud's phenomenon
- Sarcoidosis
- Sjögren's syndrome
- Stevens-Johnson syndrome
- Uveitis

^a List provided to Dynavax Technologies by FDA on 30 January 2019

^b Added by Dynavax

1.0 INTRODUCTION

This statistical analysis plan contains definitions of analysis populations and endpoints, outlines the timing of statistical analyses, and provides a comprehensive description of statistical analyses to be implemented to assess the safety and immunogenicity in healthy adults as described in Protocol DV2-PLG-01 (Amendment 5: 11 August 2023): “Phase 2, Randomized, Active-Controlled, Observer-Blinded, Multicenter Trial of the Immunogenicity, Safety, and Tolerability of rF1V Vaccine with CpG 1018 Compared with rF1V Vaccine in Adults 18 to 55 Years of Age”.

2.0 STUDY OVERVIEW

This is a phase 2, randomized, active-controlled, observer-blinded, multicenter trial of the immunogenicity, safety, and tolerability of rF1V vaccine with CpG 1018 compared with rF1V vaccine alone in adults. Approximately two hundred healthy adults 18 to 55 years of age will be enrolled to compare a two-dose regimen of rF1V with CpG 1018 administered on study Days [REDACTED] with a three-dose regimen of rF1V vaccine alone administered on [REDACTED].

The study will be conducted in 2 parts (Part 1 and Part 2). The table below outlines study drug administration in both parts. When investigational product is co-administered as 2 separate injections, the injections should be administered in close physical proximity to each other (within approximately 1 inch).

Injections will be administered by study personnel not otherwise involved in the subjects' safety evaluation. Recording and evaluation of safety information and laboratory data will be performed by observers blinded to the subjects' treatment assignment.

Part 1:

There will be 2 methods of rF1V vaccine with CpG 1018 administration:

- Group 1 (N = approximately 20): rF1V vaccine and CpG 1018 will be co-administered as 2 separate injections on Days 1 [REDACTED]
[REDACTED].
- Group 2 (N = approximately 20): bedside mix of rF1V vaccine + CpG 1018 (administered as 1 injection) and placebo will be administered as 2 separate injections on [REDACTED]

In addition, rFIV vaccine will be administered alone without CpG 1018:

- Group 3 (N=20): rF1V vaccine and placebo will be administered as 2 separate injections on Days [REDACTED]

All Groups will receive 2 injections at each treatment visit to maintain the blind.

Part 2: Part 2 will begin after immunogenicity assessments from the [REDACTED] visit in Part 1 are completed. The method of vaccine administration method that is selected from Part 1 will be evaluated in Part 2.

- Group 1 (if selected) (N=70): rF1V vaccine co-administered with CpG 1018
- Group 3 (N=70): rF1V vaccine co-administered with placebo

OR

- Group 2 (if selected) (N = 70): bedside mix of rF1V vaccine and CpG 1018
- Group 3 (N=70): rF1V vaccine

Subjects will be followed through Day 393 (Week 56)

The total duration of participation in the Screening, Treatment, and Follow-up parts of this study is up to approximately 60 weeks. This includes a Screening period beginning up to 4 weeks prior to the first study injection and End of Study (EOS) visit 56 weeks after the first study injection.

[figure not shown]
Study treatments are presented in Table 2-1. For each dose, injections are to be administered in the order specified in the table.

Table 2-1

A 10x10 grid of black and white rectangles. The grid is composed of 100 individual cells, each either entirely black or entirely white. The black cells are distributed in a non-uniform, scattered pattern across the entire area. The white cells form the background of the grid. The overall appearance is that of a sparse matrix or a binary image with a high proportion of empty space.

3.0 STUDY OBJECTIVES AND ANALYSIS VARIABLES

Objectives	Endpoints
PART 1	
Primary	

 To select one of the two methods of administration of rF1V vaccine with CpG 1018 for Part 2 by comparing humoral immunization response 28 days after the second dose of vaccine 	
 Ratio of geometric mean ELISA concentration (GMC) between rF1V vaccine with CpG 1018 and rF1V vaccine
Secondary	

 To assess the safety and tolerability of rF1V vaccine with CpG 1018 compared with rF1V vaccine 	
 Rate of reactogenicity: solicited local and systemic post-injection reactions Rate of adverse events (AEs), severe AEs, serious adverse events (SAEs), immune-mediated adverse events of special interest (AESI), and deaths
PART 2	
Primary	

 To assess the utility of a 2-dose schedule of rF1V vaccine with CpG 1018 as measured by reduction in time to onset of predicted rF1V protection To assess the [REDACTED] antibody concentration to rF1V with CpG 1018 compared with rF1V vaccine 28 days after the second dose of vaccine 	
 Predicted protection (percentage of subjects reaching the [REDACTED] threshold that corresponds to 50% predicted vaccine efficacy) after 2 doses of rF1V vaccine with CpG 1018 compared to that of 3 doses of rF1V vaccine 
Criterion for evaluation: Similar percentage of subjects reaching the [REDACTED] threshold that corresponds to 50% predicted vaccine efficacy after 2 doses of rF1V vaccine with CpG 1018 at [REDACTED] compared to that after 3 doses of rF1V vaccine [REDACTED]
 
 Ratio of geometric mean ELISA concentration (GMC) between rF1V vaccine with CpG 1018 and rF1V vaccine 28 days after the second dose 
Criterion for evaluation: 2-times increase in [REDACTED] GMC point estimate after the second dose of rF1V vaccine with CpG

	
Criterion for evaluation: GMC and seroconversion rate point estimates from rF1V vaccine with CpG 1018 to meet or exceed results from rF1V vaccine at relevant visits

	

(Days 57 85 113 / Weeks 8 12 16) as

4.0 SAMPLE SIZE CONSIDERATIONS

Part 2 primary objective 1 is to assess the utility of a 2-dose schedule of rF1V vaccine with CpG 1018 as measured by reduction in time to onset of predicted rF1V protection. The predicted protection will be based on a [REDACTED] meter threshold. Previous animal studies have established protective efficacy in animals. Since a human efficacy study is not feasible, an immunobridge from animal data to human data via the [REDACTED] test will be used to predict the protective efficacy in humans using a regression model. An initial predicted protection threshold will be calculated based on the data generated in this study in Group 3 after 3 doses of rF1V vaccine. Once the threshold is identified, it will be applied to the study groups to evaluate the Part 2 objectives. In addition to the previous animal studies conducted to establish protective efficacy, a new animal model utilizing rF1V vaccine with CpG 1018 will be developed to establish the protective level of antibody for CpG 1018 containing vaccines. Additional analyses will include a predicted protection threshold that will be calculated based on the data generated under the new animal model after 2 doses of rF1V vaccine with CpG 1018. In both instances, the animal-to-human immunobridge and the identification of the predicted protection thresholds will be documented in a separate report.

A similar approach was used to analyze the previous Phase 2a (NCT00332956) and Phase 2b (NCT01122784) study data using the animal model from the previous animal studies. Thresholds that corresponded to 50% predicted protective efficacy in humans were established for those trials. In a pooled analysis of these previous immunobridge studies, 93% (95% Clopper Pearson confidence interval [CI] = 85%, 98%) of subjects reached the predicted protection threshold.

It is assumed that a similar percentage of the subjects in Group 3 will reach the threshold identified in this study. When this threshold is applied to both Part 2 study groups, a similar lower bound of the 95% CI is desired across the groups. Table 4-1 shows the lower bound of 95% Clopper Pearson CI for different observed levels of predicted protection assuming 85 of the 90 planned subjects (Part 1 N = 20 and Part 2 N =70) will have data available for the evaluation. Thus, with a predicted protection level of 93%, the lower bound of the 95% CI would be 85%.

Table 4-1: Precision Estimate at Various Level of Predicted Protection Using Clopper Pearson CI (N=85)

Predicted Protection Level	Lower Bound of 95% CI	Upper Bound of 95% CI
95%	88%	99%
93%	85%	97%
91%	82%	96%

When the lower bound of 95% CI for the predicted protection after 2 doses of rF1V vaccine with CpG 1018 (ie, at Week 8) is similar to that after 3 doses of rF1V vaccine (ie, at Week 30), the reduction of onset time to predicted rF1V protection is demonstrated.

